7.16 Subject exit

Subjects are considered to have completed the clinical investigation if they have completed all follow-up examinations through 3 month-follow-up visit.

Currently there are no further follow up visits scheduled after the 3 month follow up. The chemical change and the lens diopter and quality are considered stable after the lens has soaked. Soaking refers to the time the water requires to penetrate into position. After 24 hours the main change will have occurred and within 7 days the soaking process is finalized.

Therefore, no follow up visit after 3 month is required for stability evaluation. Additionally, the standard follow up visit period for traditional multifocal intraocular lens implantation studies is 3 month. We are aware that the neuroadaptation might take longer but this would be beyond the scope of this pilot trial.

Exhibit B lists 3 accelerated aging studies which have been conducted to verify lens stability

The current study design is focused on a one-time treatment, invitro treatments have shown that multiple treatments are possible inside the same IOL. In an unsatisfactory outcome or with deterioration of near or far vision, a future possibility of an additional treatment would be possible. The conditions of the section treatment will still need to be defined and might be adjusted with future studies. In the laboratory successful additional treatments have been performed. Which included adding a cylindrical lens to a multifocal treatment, an additional spherical treatment to a multifocal treatment or adding or removing a multifocal treatment to a spherical lens which already had received a multifocal treatment.

7.16.1 Subject withdrawal or discontinuation

Subject participation is voluntary; any subject may discontinue participation in the clinical The clinical investigation will be conducted without prejudice, and subjects have the option to withdraw from the study voluntarily or be withdrawn by the Investigator or Sponsor. The Investigator has the authority to terminate subjects from the clinical investigation only if their continued participation in the study Treatment regimen would pose a risk to their health

 Clinical Investigation Plan PL-RIS01	Page no.	34 z 55
	Version	02
	Date	2023-07-18

and/or welfare. Efforts will be made to encourage subjects who wish to withdraw their consent to return to the clinical site for an exit visit assessment before officially withdrawing.

Subjects may be discontinued from the clinical investigation only when there are no other viable options. Reasons for discontinuation include, but are not limited to:

- Screen failure
- Subject's withdrawal of consent prior to Treatment
- Inability to continue participating in the study
- Subject's death
- Subject discontinued by the investigator (e.g., inadequate dilation on the surgical day)

A subject exit form must be completed for all subjects who complete, discontinue, or are terminated from the clinical investigation, providing the reason for their exit. Discontinued subjects will still be included in the analysis up until the point of their exit. Whenever feasible, all necessary clinical assessments will be conducted before the subject exits the investigation, even if the assessment was not originally scheduled for that particular visit.

The subject numbers assigned to discontinued subjects will not be reassigned to new participants.

Discontinued subjects will not be replaced, except in cases where they discontinued before receiving study Treatment.

7.16.2 Lost to Follow up

The clinical site is committed to conducting diligent follow-up on subjects who do not attend their scheduled examinations. A minimum of three documented attempts will be made to contact the subject, using methods such as telephone, email, or regular mail. If a subject remains unresponsive to these follow-up attempts, they will be categorized as "lost to follow-up." It is important to note that subjects who are classified as lost to follow-up will not be replaced with new participants.

To ensure proper documentation and record-keeping, a subject exit form must be completed for every subject who completes the study, discontinues their participation, or is terminated from the clinical investigation. The exit form should include the reason for their exit from the study, providing clarity and transparency regarding their status and any contributing factors.

 PERFECT LENS PL-RIS01	Clinical Investigation Plan	
	Page no.	35 z 55
	Version	02
	Date	2023-07-18

7.17 Examination matrix

Examination data	Visit 1 - Screening	Visit 2 - Treatment	Visit 3 – 1W follow up	Visit 4 – 1M follow up	Visit 5 – 3M follow up
Informed consent	X				
Demographics, medical history	X				
Inclusion and exclusion criteria	X				
IOL laser adjustment		X			
Biometry measurements	X				
Slit lamp examination	X		X	X	X
Objective refraction	X		X	X	X
Intraocular pressure	X		X	X	X
Monocular UDVA, UIVA, UNVA	X		X	X	X
Binocular UDVA, UIVA, UNVA	X		X	X	X
Subjective manifest refraction	X		X	X	X
Monocular CNVA (with near addition)	X		X	X	X
Monocular CDVA, DCIVA, DCNVA	X		X	X	X
Binocular CDVA, DCIVA, DCNVA	X		X	X	X
Defocus curve	X		X	X	X
Contrast sensitivity	X				X
OCT	X			X	X
I-Trace	X				
Fundus examination	X			X	X
QoV questionnaire	X				X
Spectacle independence questionnaire	X				X
Adverse events, concomitant medication	X		X	X	X

CONFIDENTIAL

 Clinical Investigation Plan PL-RIS01	Page no.	36 z 55
	Version	02
	Date	2023-07-18

7.18 Clinical-investigation-related procedures

7.18.1 Objective and subjective refraction

The assessment of refraction, which includes sphere (D), cylinder (D), and axis (°), will be conducted through subjective and objective methods. Objective refraction will follow standard clinical practice and will be performed by the Investigator or trained staff. Subjective testing will be conducted using trial frames instead of a phoropter. Consistency in the refractive technique should be maintained throughout the entire study duration. Test optotypes such as Sloan letters (e.g., ETDRS charts) will be used.

The cylinder value should be recorded in negative notation. Cylinder refraction should be performed for every patient. If the cylinder refraction is zero, the cylinder axis should be marked as not applicable. A pre-sign for the sphere is only necessary for negative values. If no pre-sign is entered, it indicates a positive value.

7.18.2 Measurement of visual acuities

Visual acuity assessment will be performed monocularly and binocularly using the ETDRS charts in photopic conditions. The device used will be document in the study documentation. For the intermediate and near VAs the ETDRS chart hand held charts (VectorVision) will be used. The following test will be performed as per the examination schedule.

- Uncorrected distance visual acuity (UDVA)
- distance corrected visual acuity (CDVA)
- Uncorrected intermediate visual acuity at 66 cm (UIVA)
- Distance corrected intermediate visual acuity (DCIVA) at 66 cm
- Uncorrected near visual acuity at 40 cm (UNVA)
- Corrected near visual acuity at 40 cm (CNVA)
- Distance corrected near visual acuity (DCNVA) at 40 cm

7.18.3 Biometry measurement

The equipment for assessing the clinical investigation variables is to the discretion of the investigator and his standard of care. For taking the biometry measurements the IOL Master 500 or 700 by Carl Zeiss Meditec AG should preferably be used though.

7.18.4 Aberrometer measurement - iTrace

Corneal, internal and total aberrometer data will be collected using iTrace device as per the standard operating procedure. Care will be taken to naturally induce as big pupil size as possible. No dilation will be used in this examination. The outcome values will be corneal, internal and total aberrometry data – Higher Order Aberration, spherical aberration at 3 mm pupil and 4 mm pupil size.

7.18.5 Defocus curve

To assess the defocus curve the same optotype as for the distance visual acuity will be used. The test will be performed with the best distance corrected refraction and spherical additions

 PERFECT LENS PL-RIS01	Clinical Investigation Plan	Page no.	37 z 55
		Version	02
		Date	2023-07-18

between -5.0 D to +1.5 D in 0.5 D steps. Defocus curve will be performed monocularly. The patient will be presented with the spherical additions in the order from -5.0 D to +1.5 D.

7.18.6 Contrast sensitivity

Contrast sensitivity testing will be performed monocularly with the distance-corrected study eye under photopic with glare, mesopic and mesopic with glare conditions using CSV 1000. The testing will be performed at spatial frequencies of 3, 6, and 12 and 18 cycles/degree.

Mesopic contrast sensitivity testing (3 cd/m²) using mesopic filter installed in the patient trial frame, will be performed prior to the photopic testing (85 cd/m²). A minimum of 5 minutes should be provided for the patient's eye dark adaptation before the beginning of the mesopic contrast testing in a room with photopic light conditions.

The ambient illumination should be lower or at most equal to the chart luminance. The mesopic testing without glare will be performed first before testing with glare source provided with the testing device.

7.18.7 Fundus examination

To examine the retinal integrity and document the safety of the procedure a full fundus examination will be performed using a slit lamp and dilated pupil for a clear view.

7.18.8 Slit lamp examination

Slit lamp examination will be performed using a slit lamp biomicroscope. The subject will be seated. During this examination the eyes might be dilated depending on doctors' decision. The following will be examined during the examination conjunctiva, cornea, anterior chamber, iris, eyelid. Magnification will be consistent with standard clinical practise.

The observation will be graded as normal or abnormal. In case of abnormal observations subjective graded according to the grading scales will be used. The abnormal grading will then be graded as clinical significant or not clinically significant. In case of clinically significant observation the event will be specified and will be collected as adverse events.

CORNEAL STATUS

1. Epithelial erosion, grade

- 0: Absent
- I: Minimal
- II: Mild
- III: Moderate
- IV: Marked
- V: Severe

2. Corneal edema, grade

0: No corneal edema	0: Completely clear cornea
1: < 3 mm in diameter	1: Focal exudation in stroma

 PERFECT LENS PL-RIS01	Clinical Investigation Plan	Page no.	38 z 55
		Version	02
		Date	2023-07-18

2: > 3 mm in diameter and < 5 mm in diameter 3: > 5 mm in diameter	2: Increase in stromal thickness 3: Severe increase in stromal thickness and exudation
---	---

SIGN OF INFLAMATION

1. Anterior chamber cells, grade (Cells in field (size 1 mm by 1 mm slit beam)

0 < 1 0.5+ 1-5 1+ 6-15 2+ 16-25 3+ 26-50 4+ > 50

2. Anterior chamber flare, grade

0 None 1+ Faint 2+ Moderate (iris/lens details clear) 3+ Marked (iris/lens details hazy) 4+ Intense (fibrin/plastic aqueous)
--

3. Vitreous cells, grade

0 No cells 0.5+ 1-10 1+ 11-20 2+ 21-30 3+ 31-100 4+ >100

4. Hypopyon, grade

H0 Absent + Less than 2 mm ++ Less than 5 mm (filling up half of anterior chamber) +++ 5 mm or more (filling more than half of anterior chamber)

 PERFECT LENS PL-RIS01	Clinical Investigation Plan	Page no.	39 z 55
		Version	02
		Date	2023-07-18

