4.3 Description of the investigational device

4.3.1 Parts of the Device

The Perfector consists of (i) a femtosecond laser, (ii) a scanner capable of using light to capture two and three-dimensional images from within optical scattering media, (iii) a scanner (the "OCT"), which performs a non-invasive imaging test that uses light waves to take cross section pictures of the interior of the eye and is able to locate the implanted intraocular lens, (iv) an optical focusing system using lenses and mirrors, (v) an objective lens, (vi) a computer, (vii) a camera, (viii) proprietary software, which controls the relationship between the scanners, the laser and the focusing system, (ix) non-proprietary software produced by the manufacturers of the laser, 2D scanner, computer, and OCT, (x) patient attachment which attaches patient to system for Treatment, and (xi) a power supply, which includes an emergency power supply (the "UPS"). All components, except the proprietary software, are "off the shelf" items which are used in medical devices in the marketplace today. The Perfector is mounted upon a movable cart that measures 5 feet wide by 2½ feet deep, by 6 feet high. It is powered by a 220-240 VAC mains power supply.

 PERFECT LENS	Clinical Investigation Plan	Page no.	13 z 55
PL-RIS01		Version	02
		Date	2023-07-18

[figure not shown]

Figure 1 Scheme of the Perfector device

The Device alters the IOL by changing a thin disc in the interior of the IOL. It directs laser light to the IOL and alters the hydrophilicity of the treated area. By altering hydrophilicity of this treated area, the Device is able to create multi focality within the implanted lens. The exposure of the interior of the IOL to the femtosecond laser energy increases the hydrophilicity that is within the IOL by creating additional hydroxyl and acid groups. These acid and hydroxyl groups are hydrophilic and create a gradient which attracts water molecules. The addition of the water molecules changes the refractive properties of the IOL by reducing the refractive index of the treated area.

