5.1.1 Laser Energy

In the proposed study, Perfector intends to use, low-fluence, low-dose femtosecond laser energy at a fraction of the energy of used in capsulotomies. The chart of energy used is set forth below. The Treatment was used to make refractive changes to implanted lenses in a study in Panama. After an injury to a patient in the initial Treatment, the energy used in the Treatment has been reduced by over 90%. There was no adverse event in the last 12 patients treated with the lower energy levels. The energy used to create near vision in the implanted IO is less than the revised energy levels used to correct refractive errors in Panama. The energy used in this Study will less than the revised energy levels used in Panama, where there were no injuries.

The energy delivered in the Study is non-ablative – i.e., it does not cut eye tissue, but only modifies the refractive index of the implanted IOL. Unlike lens explantation or post-cataract

 PERFECT LENS PL-RIS01	Clinical Investigation Plan	Page no.	17 z 55
		Version	02
		Date	2023-07-18

refractive surgery (LASIK/PRK), low-fluence femto-laser adjustment will not expose the eye to the risks of endophthalmitis, infection and many of the anterior segment and corneal problems associated with these procedures.

The Company has conducted an extensive laser safety study which is included in the investigator's brochure. The laser safety study states that the lack of energy and location of the energy focus is not hazardous to the eye. It is important to note that the procedure does not target any ocular tissue.

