5.2 Pre-clinical testing

Summary of the preclinical testing that has been performed on the investigational device, together with an evaluation of the results of such testing, justifying its use in human subjects.

The index for all pre-clinical tests is attached as Exhibit B and is available for review. In summary:

The main preclinical material was the J&J material which is used during this study. The preclinical study literature is listing the J&J models (AAB00, ZCB00 or ZMB00). Additionally, the initial clinical study was performed on the same J&J material.

Study Name	Comment	Page # in Exhibit B	Material
Laser Safety Study	Optical hazard evaluation	1	NA
Exhaustive Extraction Study	No substantial differences between treated vs. untreated	43	J&J material
Leachable Study	No additional leachable created by the Treatment	53	J&J material

 PERFECT LENS PL-RIS01	Clinical Investigation Plan	Page no.	18 z 55
		Version	02
		Date	2023-07-18

Bubble Creation Study	Bubbles created during Treatment contained no cytotoxic species	114	J&J material
Photostability Study	Showed no effect on treated IOL	179	J&J material
Hydrolytic Study	Accelerated Aging Study showed Diopter Stability and no additional leachable	184	J&J material
Glistening Study	Optimized Treatment created no glistening	208	J&J material
Safety Sensor Test using Start Test installed in Device	Safety Sensors do identify problems in the Device	213	NA
Inorganic Soluble Study	Laser adjusted lens free of significant amounts of inorganic solubles within FDA standards	219	J&J material
YAG Study	YAG Treatment had no adverse effects on adjusted IOL	241	J&J material
Intramuscular implantation of treated IOL Study	No calcifications created	280	J&J material
Patient Attachment Study	Minimal cytotoxicity, sensitization and ocular irritation	326	NA
Physical Property Study	Treatment had no effect on physical properties of IOL	413	J&J material
Light Transmission Study	No significant reduction in light transmission	441	Zeiss hydrophobic material
Light Scattering Study	No significant increase in light scatter	446	Zeiss hydrophobic material

CONFIDENTIAL

 PERFECT LENS PL-RIS01	Clinical Investigation Plan	Page no.	19 z 55
		Version	02
		Date	2023-07-18

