7.3 Other outcome measures

The following is a list of additional outcomes measures:

- Uncorrected and corrected distance visual acuity (UDVA)
- Uncorrected and corrected intermediate visual acuity at 66 cm (UIVA)
- Uncorrected near visual acuity at 40 cm (UNVA)
- Corrected near visual acuity at 40 cm (CNVA)
- Defocus curve
- Contrast sensitivity
- Subjective refraction
- Near addition
- Slit Lamp examination findings
- Fundus examination findings
- Intraocular pressure
- Spectacle independence questionnaire

 PERFECT LENS	Clinical Investigation Plan	Page no.	27 z 55
PL-RIS01		Version	02
		Date	2023-07-18

- QoV patient questionnaire
- Treatment satisfaction
- Adverse Events
- Device deficiency

Note: All visual acuity assessment can be performed monocularly and binocularly as per the examination matrix and speciation of the measurements.

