7.18.10 Optical coherence tomography (OCT)

Anterior segment OCT and fundus OCT will be taken as per the standard clinical practise. The findings will be recorded in the source documentation as either normal or abnormal. In case of abnormal findings the observation will be evaluated as clinical significant or not clinically significant.

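### The slit-lamp examination names five structures and six grading scales but not the treated IOL or the posterior capsule, so lens changes are not systematically recorded

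*Protocol*

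**What the plan says.** Section 7.18.8 lists what is examined at the slit lamp: "The following will be examined during the examination conjunctiva, cornea, anterior chamber, iris, eyelid". Each observation is rated normal or abnormal. For abnormal ones, "In case of abnormal observations subjective graded according to the grading scales will be used", followed by a judgement of clinical significance. Significant observations are collected as adverse events. Dilation is optional: "During this examination the eyes might be dilated depending on doctors' decision".

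Section 7.3 names "Slit Lamp examination findings" among the outcome measures. The matrix in 7.17 schedules the slit lamp at screening, 1 week, 1 month and 3 months, and sections 7.9 and 7.11 to 7.13 agree.

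On where the treatment acts, section 4.3.1 says: "The Device alters the IOL by changing a thin disc in the interior of the IOL". Section 5.1.1 adds: "It is important to note that the procedure does not target any ocular tissue". The bench programme in section 5.2 examined the treated lens for, among other things, bubbles, glistening, light transmission and light scatter. The glistening result reads "Optimized Treatment created no glistening".

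Section 7.18.10 covers anterior-segment and fundus OCT: "The findings will be recorded in the source documentation as either normal or abnormal". Abnormal findings are then judged clinically significant or not. The section names no structure to be read.

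**The concern.** The structure the device is meant to alter is the one missing from the examination that documents the state of the anterior eye. If 7.18.8 is followed as written, the study report can show normal slit-lamp findings at every visit without anyone having been asked to grade the treated lens. A reader of that report would naturally take normal findings to include the lens.

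Attribution is also at stake. Each eye serves as its own control (7.1), and the protocol itself treats lens condition and position as important. Section 6.2.4 says multifocal IOLs are sensitive to decentration, and section 6.2.1 names IOL movement during Treatment as the second risk. If CDVA, DCIVA or contrast sensitivity falls after Treatment, the first questions will be whether the lens is hazy, whether the treated zone is off-centre, and whether the capsule has opacified. Without a graded baseline and follow-up entry for these, the answers depend on what individual examiners happened to note.

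**Working it through.** The protocol gives no figure to reproduce. The check sets the slit-lamp specification beside every other place where an IOL or capsule finding could be required.

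**Slit lamp (7.18.8)**

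- Structures named: conjunctiva, cornea, anterior chamber, iris, eyelid. That is 5, of which 0 are the IOL or capsule.
- Grading scales: epithelial erosion, corneal edema, anterior chamber cells, anterior chamber flare, vitreous cells, hypopyon. That is 6, of which 0 are for the IOL or capsule. The lens appears only as a visual reference within the flare scale.
- The visit sections (7.9, 7.11 to 7.13) ask for slit-lamp biomicroscopy without naming structures, so 7.18.8 alone defines its content.

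**Other routes**

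| Route | Timing | IOL or capsule finding required? |
|---|---|---|
| Anterior-segment OCT (7.18.10) | Matrix: screening, 1 and 3 months. Also in the 7.9 list; absent from the 7.12 and 7.13 lists | No; overall rating, structures not named |
| iTrace (7.18.4) | Screening only (7.9, 7.17) | No; no post-Treatment measurement |
| Fundus examination (7.18.7) | Listed at all three follow-up visits in 7.11 to 7.13; the matrix omits 1 week | No; aimed at the retina |
| Adverse events (14.6) | Throughout | No; the listed examples are corneal, inflammatory, macular, retinal and pressure events, though the list is open-ended |
| Device deficiency (7.3, 14.1.3) | Throughout | No; arises only if a problem is noticed |

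On OCT, the 1-week list in 7.11 and the matrix agree, since neither schedules it. The conflict is confined to 7.12 and 7.13, where the matrix marks OCT and the procedure lists do not.

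**Size**

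Inputs: up to 24 eyes (8.1) and slit-lamp visits from 7.17.

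- Post-Treatment: 24 eyes x 3 visits = 72 examinations.
- Baseline: 24 eyes x 1 visit = 24 examinations.
- Total: 72 + 24 = 96.

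Only the 72 could miss a change caused by Treatment. The 24 matter because a later finding cannot be called new without a baseline entry.

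**Bench evidence**

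The results in 5.2 are favourable: no glistening with the optimised Treatment, no cytotoxic species in the bubbles, no significant increase in scatter or reduction in transmission. The scatter and transmission studies, however, are listed against a Zeiss hydrophobic material, while 5.2 says the J&J material is the one used in this study. For those two properties, the listed tests do not bear directly on the trial lens.

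**The case against.** The strongest reply is that the lens is not left unobserved. Anterior-segment OCT is planned before and after Treatment, with the same two-step scoring (normal/abnormal, then clinical significance) that the fix would use. The fundus examination is done at the slit lamp through a dilated pupil, so the examiner looks through the IOL and capsule. All ocular adverse events must be reported, device deficiencies are collected, and acuity, defocus and contrast testing would show a functional effect. The list in 7.18.8 also looks loosely drafted: it is followed by a scale for vitreous cells, although the vitreous is not one of the five structures. The trial is a 12-patient descriptive pilot, and no primary endpoint or analysis depends on this item. The eCRF is not shown and may contain a lens field.

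Much of this stands, and it limits the point. A reader might infer that lens damage would go undetected, or that a poor acuity result could not be traced to the lens. The documents do not support either reading, because the routes above could reveal a problem. Nor is OCT a weak substitute because of its scale or a missing baseline: the scale is adequate and a screening OCT is required. A reader might also infer that the sponsor expects lens damage, but the stated bench results point the other way.

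What the reply does not supply is a requirement. None of these routes obliges anyone to record an IOL or capsule finding. The stray vitreous scale shows that list and scales disagree, but it does not bring the IOL into the examination. Nor can an analysis plan make up for observations that were never collected.

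**Conclusion.** The point holds as a gap in systematic recording. Section 7.18.8 specifies a set of structures that leaves out the treated lens and the capsule behind it, and no post-Treatment procedure elsewhere requires a finding on either. Up to 72 post-Treatment examinations and 24 baseline examinations are affected, assuming full enrolment of 24 eyes and no missed visits. The consequence is that a listed safety outcome can be reported as clean with the lens ungraded, and that a loss of acuity or contrast becomes harder to attribute to lens haze, decentration or capsule opacity.

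This rests on the protocol text alone; a lens field in the eCRF would reduce the practical effect but would leave the protocol to be aligned with it. The point does not touch the primary endpoints, the sample size or the descriptive analysis. The change is worth making because it is small and concerns the structure the device acts on.

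**What to change.** - In 7.18.8, add to the structures examined: IOL (clarity, glistenings or bubbles, visible treatment zone, centration) and posterior capsule.
- Apply the section's existing normal/abnormal rating and clinical-significance judgement to each, at baseline and at every follow-up visit, so that significant findings reach the adverse-event record by the route already in place.
- Provide matching CRF and worksheet fields.
- Reconcile the OCT entries: the matrix in 7.17 marks OCT at 1 and 3 months, while the lists in 7.12 and 7.13 omit it.

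The cost is a few lines of protocol text, a few CRF fields, and a little extra examination and recording time per eye. Instrument, visits and examiner stay the same. Because 7.18.8 leaves dilation to the doctor, the sponsor should confirm with the investigator that each added item can be assessed under the conditions of the examination as written.
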